6.0 Complaints

A Complaint is any written, electronic, or oral communication that alleges deficiencies related to the physical characteristics, identity, quality, purity, potency, durability, reliability, safety, effectiveness, or performance of a product/device after it is released for distribution.

The investigational product in this trial contains both:

- Biologic compound(s) and
- Device component(s) (pre-filled syringe).

Complaints associated with any component of this investigational product must be reported to the Sponsor (Section 6.2.2). For adverse events, please refer to Sections 6.1 through 6.1.6. For product complaints, please refer to Section 6.2.

Section 6.0 through 6.6

Section number and title previously read:

6.0	Adverse Events
6.1	Definitions
6.1.1	Adverse Event
6.1.1.1	Uveitis-Related Events
6.1.2	Serious Adverse Events
6.2	Adverse Event Severity
6.3	Relationship to Study Drug
6.4	Adverse Event Collection Period

6.5 Adverse Event Reporting

Has been changed to read:

6.0 Complaints

6.1 Medical Complaints

6.1.1 Definitions

6.1.1.1 Adverse Event

6.1.1.1.1 Uveitis-Related Events

6.1.1.2 Serious Adverse Events

6.1.2 Adverse Event Severity

6.1.3 Relationship to Study Drug

6.1.4 Adverse Event Collection Period

6.1.5 Adverse Event Reporting

Section 6.5 Adverse Event Reporting

Previously read:

In the event of a serious adverse event, and additionally, any non-serious event of malignancy in subjects 30 years of age and younger, whether related to study drug or not, the physician will notify the AbbVie Immunology Clinical Safety Management Team within 24 hours of the physician becoming aware of the event by entering the serious adverse event or non-serious event of malignancy in subjects 30 years of age and younger data into the electronic data capture (EDC) system. Serious adverse events and non-serious events of malignancy in subjects 30 years of age and younger, that occur prior to the site having access to the Rave system should be faxed to the Immunology Clinical Safety Team within 24 hours of being made aware of the adverse event.

FAX to: 

For serious adverse event concerns, contact the Immunology Safety Team at:

Immunology Safety Team
Immunology Development

AbbVie
[name]
[name]
USA

Fax: 
Safety Hotline: 
Email: 

For any subject safety concerns, please contact the AbbVie Medical Monitors listed below:

For US, Canada, Latin America and Japan

For Europe, Israel and Australia

In the EU, the sponsor will be responsible for Suspected Unexpected Serious Adverse Reactions (SUSAR) reporting for the Investigational Medicinal Product (IMP) in accordance with Directive 2001/20/EC. The reference document used for SUSAR reporting in EU countries for adalimumab will be the most current version of the Investigator's Brochure.

Has been changed to read:

In the event of a serious adverse event, and additionally, any nonserious event of malignancy in subjects 30 years of age and younger, whether related to study drug or not, the investigator will notify Clinical Pharmacovigilance within 24 hours of the site being aware of the event by entering the serious adverse event or nonserious event of malignancy in subjects 30 years of age and younger data into the electronic data capture (EDC) system. Serious adverse events and nonserious events of malignancy in subjects 30 years of age and younger, that occur prior to the site having access to the RAVE system or if RAVE is not operable should be sent to Clinical Pharmacovigilance within 24 hours of site being made aware of the adverse event.

FAX to:	
Email:	

For serious adverse event concerns, contact the Immunology Safety Team at:

Immunology Safety Team
Immunology Development

AbbVie
[name]
[name]
USA

Fax:
Safety Hotline:
Email:

For any subject safety concerns, please contact the AbbVie Medical Monitors listed below:

For US, Canada, and Latin America:

For Europe, Israel, Australia and Japan:

Secondary Contact for Japan (Regional Medical Monitor):

██████████ and ██████████ cover for each other. For any subject safety concerns or medical emergencies in which both medical monitors are unavailable, please call the following central back-up number:

Phone: ██████████

In the EU, the sponsor will be responsible for Suspected Unexpected Serious Adverse Reactions (SUSAR) reporting for the Investigational Medicinal Product (IMP) in

accordance with Directive 2001/20/EC. The reference document used for SUSAR reporting in EU countries for adalimumab will be the most current version of the Investigator's Brochure.

Section 6.6 Pregnancy

Section number and title previously read:

6.6 Pregnancy

Has been changed to read:

6.1.6 Pregnancy

Section 6.2 Product Complaint

Add: new section and text, renumber subsequent sections

6.2 Product Complaint

6.2.1 Definition

A Product Complaint is any Complaint (see Section 6.0 for the definition) related to the biologic or drug component of the product or to the medical device component(s).

For a product this may include, but is not limited to, damaged/broken product or packaging, product appearance whose color/markings do not match the labeling, labeling discrepancies/inadequacies in the labeling/instructions (example: printing illegible), missing components/product, device not working properly, or packaging issues.

For medical devices, a product complaint also includes all deaths of a patient using the device, any illness, injury, or adverse event in the proximity of the device, an adverse event that could be a result of using the device, any event needing medical or surgical intervention including hospitalization while using the device and use errors.

Any information available to help in the determination of causality by the device to the events outlined directly above should be captured.

6.2.2 Reporting

Product Complaints concerning the investigational product and/or device must be reported to the Sponsor within 24 hours of the study site's knowledge of the event via the Product Complaint form. Product Complaints occurring during the study will be followed-up to a satisfactory conclusion. All follow-up information is to be reported to the Sponsor (or an authorized representative) and documented in source as required by the Sponsor. Product Complaints associated with adverse events will be reported in the study summary. All other complaints will be monitored on an ongoing basis.

Product Complaints may require return of the product with the alleged complaint condition (syringe). In instances where a return is requested, every effort should be made by the investigator to return the product within 30 days. If returns cannot be accommodated within 30 days, the site will need to provide justification and an estimated date of return.

The description of the complaint is important for AbbVie in order to enable AbbVie to investigate and determine if any corrective actions are required.

Section 7.0 Protocol Deviations

First paragraph previously read:

The Investigator should not implement any deviation from the protocol without prior review and agreement by the Sponsor and in accordance with the Independent Ethics Committee (IEC)/Independent Review Board (IRB) and local regulations, except when necessary to eliminate an immediate hazard to study subjects. When a deviation from the protocol is deemed necessary for an individual subject, the Investigator must contact the AbbVie Medical Monitor listed in Section 1.0 and Section 6.5.

Has been changed to read:

AbbVie does not allow intentional/prospective deviations from the protocol. The Principal Investigator is responsible for complying with all protocol requirements, and applicable global and local laws regarding protocol deviations. If a protocol deviation

occurs (or is identified) after a subject has been enrolled, the Principal Investigator is responsible for notifying Independent Ethics Committee (IEC)/Independent Review Board (IRB) regulatory authorities (as applicable), and the AbbVie Clinical Monitor(s) assigned to your site. Alternative contacts are as follows:

Alternate Contacts

North America, Latin America, and Japan Europe, Israel, and Australia

Such contact must be made as soon as possible to permit a review by AbbVie to determine the impact of the deviation on the subject and/or the study.

Section 7.0 Protocol Deviations

Delete: third paragraph

Such contact must be made as soon as possible to permit a review by AbbVie to determine the impact of the deviation on the subject and/or the study. Any significant protocol deviations affecting subject eligibility and/or safety must be reviewed and/or approved by the IEC/IRB and regulatory authorities, as applicable, prior to implementation.

Appendix E. Subject Dosing Diary
Last page of diary previously read:

M11-327

Subject Identification Number

Adalimumab Dosing Diary

Date	Week #	Kr. Number	Time of Study Drug Administration	Was the entire volume injected? (Y/N)	Initials of Person Administering Study Medication	Comments
19-Mar-13	EXAMPLE	101010	9:35	Y	MM	none
	Week 276					
	Week 278					
	Week 280					

20120312 Dosing Diary Uveitis
 White Copy (site)

Abbott Laboratories

Adalimumab Dosing
 Yellow Copy (diary)

Has been changed to read:

M11-327

Subject Identification Number

Adalimumab Dosing Diary

Date	Week #	Kit Number	Time of Study Drug Administration	Was the entire volume injected? (Y/N)	Initials of Person Administering Study Medication	Comments
19-Mar-13	EXAMPLE	101010	9:35	Y	MM	none
	Week 276					
	Week 278					
	Week 280					
	Week 282					
	Week 284					
	Week 286					
	Week 288					
	Week 290					

20120312 Dosing Diary Uveitis
White Copy (site)

Abbott Laboratories

Adalimumab Dosing
Yellow Copy (diary)

Appendix F. AREDS 2008 Clinical Lens Opacity Grading Procedures

Delete: last paragraph

Website: <http://eyephoto.opth.wisc.edu/ResearchAreas.html>

Appendix K. Japan Appendix

Section 5.3.1.1 Study Procedures

Subsection Chest X-ray (CXR)

Second paragraph previously read:

If a subject has a positive TB test at Baseline or Week 42, 90, 138, 186, or 234, subjects will undergo a standard CXR (posterior-anterior [PA] and lateral views) to rule out the presence of TB or other clinically relevant findings.

Has been changed to read:

If a subject has a positive TB test at Baseline or Week 42, 90, 138, 186, 234, 282, or 330, subjects will undergo a standard CXR (posterior-anterior [PA] and lateral views) to rule out the presence of TB or other clinically relevant findings.

Appendix K. Japan Appendix

Section 5.3.1.1 Study Procedures

Subsection Dispense Study Drug

Second paragraph previously read:

Subjects in Japan will be administered the study drug by the medical staff throughout the study when the dose of prednisone or prednisone equivalent is ≤ 10 mg/day to secure the safety of the subjects.

Has been changed to read:

Subjects in Japan will be administered the study drug at the investigative site throughout the study when the dose of prednisone or prednisone equivalent is > 10 mg/day to secure the safety of the subjects.

**07 July 2016**

## Rationale for Changes

The changes to SAP Amendment 1 dated 09 March 2015 described in this amendment were necessary to include additional analyses.

## Summary of Changes

- Section 3.0: updated protocol amendment, changed notation for non-infectious intermediate, posterior and panuveitis and deleted IDMC section, since it was finished after second pivotal study terminated (Study M10-880)
- Section 4.1: changed notation for non-infectious intermediate, posterior and panuveitis
- Section 4.2: changed notation for non-infectious intermediate, posterior and panuveitis and changed study termination date
- Section 6.2: corrected First Rx Day column entry
- Section 6.3: added specification for interim analysis
- Section 7.1: changed labels for age variables
- Section 7.5: removed 'at baseline' next to IMMs and added abbreviation for corticosteroids
- Section 8.0: added additional category for interim analysis
- Section 10.1: added pooled analysis for efficacy variables
- Section 10.2: added new efficacy variables and additional analyses
- Section 10.4: added subgroups for some efficacy variables
- Section 11.1: added E/100PY for subgroup analysis of AEs and further subgroups
- Section 13.0: added new abbreviations

Full details of all changes are given in Section 15.0.

The amended Statistical Analysis Plan now reads as follows:

---

### **3.0                   Introduction**

The SAP will provide details to further elaborate statistical methods as outlined in the protocol of Study M11-327, "A Multicenter Open-Label Study of the Long-term Safety and Efficacy of the Human Anti-TNF Monoclonal Antibody Adalimumab in Subjects with Non-infectious Intermediate, Posterior, or Panuveitis" and will describe analysis conventions to guide the statistical programming work. The analysis plan is based on protocol amendment 10 dated as of 04 June 2015.

Analyses described in this SAP comprise the analyses that will be performed by AbbVie after the study (including the total set of subjects from Japan and non-Japan) has been terminated.

All analyses will be performed using SAS®.

### **4.0                   Study Objectives, Design and Procedures**

#### **4.1                   Objectives**

[figure not shown]
The primary objective of this study is to evaluate the long-term safety of adalimumab 40 mg given every other week (eow) subcutaneously (SC) in subjects with non-infectious intermediate, posterior, or panuveitis who participated in Protocol M10-877 or Protocol M10-880. Long-term efficacy will also be assessed.

#### **4.2                   Design Diagram**

This study is a Phase 3, open-label multicenter study designed to evaluate long-term safety and efficacy of adalimumab in adult subjects with non-infectious intermediate, posterior, or panuveitis who have either discontinued from Study M10-877 or Study M10-880 for having met "Treatment Failure" criteria or have successfully completed Study M10-877 or Study M10-880. Subjects, who prematurely discontinued from Study M10-877 or Study M10-880 for reasons other than for Treatment Failure as defined in the parent protocol, will not be eligible for this study. Study visits will occur at Week 0, 2, 4, 8, 12, 18 and every 12 weeks thereafter. Visits will occur every 12 weeks

---

following Week 66 until the end of the study. The entire study will be terminated in March 2018.

\* Visits will occur every 12 weeks following Week 66 until the end of the study (not to exceed 15 March 2018).

## 5.0 Analysis Sets

The following analysis sets will be used for the analysis.

### 5.1 Definition for Analysis Sets

Safety analyses will be conducted in the safety set. The safety set includes all subjects who received at least one dose of study medication.

Efficacy analyses will be provided for the Intent-to-Treat (ITT) set. The ITT set includes all subjects who received at least one dose of study medication. In addition, the following subjects will be excluded from the ITT set:

- Subjects who developed Exclusion Criterion No. 5 ("Subject with proliferative or severe non-proliferative diabetic retinopathy or clinically significant macular edema due to diabetic retinopathy") during the study.

- Subjects undergoing a cataract surgery during the study.
- Subjects that had previous vitrectomy or are vitrectomized during the study.
- Subjects [REDACTED] from Investigator [REDACTED] ([REDACTED] France) will be excluded because of incomplete efficacy source data in studies M10-877 and M10-880.
- Subjects from Investigator [REDACTED] ([REDACTED] USA) will be excluded because of general compliance issues in studies M10-877 and M10-880.

Both, the ITT set and the safety set will include subjects recruited in and outside Japan.

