- Proportion of subjects at each study time point without a worsening of BCVA by ≥ 15 letters on the ETDRS in both eyes relative to Baseline for subjects who had inactive uveitis when they entered the study and to Week 8 for subjects who had active uveitis when they entered the study.
- Percent change in central retinal thickness (1 mm subfield) in each eye at each study time point relative to Baseline for subjects who had inactive uveitis when they entered the study and to Week 8 for subjects who had active uveitis when they entered the study.
- Change in NEI Visual Functioning Questionnaire (VFQ-25) score at each study time point relative to Baseline for subjects who had inactive uveitis when they entered the study and to Week 8 for subjects who had active uveitis when they entered the study.
- Proportion of subjects at each study time point achieving a $\geq 50\%$ reduction in immunosuppression load relative to Baseline for subjects who had inactive uveitis when they entered the study and to Week 8 for subjects who had active uveitis when they entered the study.

Other efficacy variables include: Work Productivity and Activity Impairment Questionnaire: Specific Health Problem Questionnaire (WPAI-SHP), EuroQol-5D Questionnaire (EQ-5D) and Health Resource Utilization Questionnaire (HRU).

Safety: Safety will be assessed by adverse events, laboratory data, physical examinations and vital signs throughout the study.

Statistical Methods:

Efficacy: Efficacy analyses will be based on the Intent to Treat (ITT) set which includes all subjects that received at least one dose of study drug in Study M11-327. All statistical analyses will be descriptive. Results will be stratified between subjects who entered into the study with active versus inactive uveitis. For subjects who had active uveitis when they entered the study, the efficacy analyses will start at Week 8. For subjects who had inactive uveitis when they entered the study, the efficacy analyses will start at Week 0. Continuous variables will be summarized by the number of non-missing observations, mean, standard deviation, median, quartiles, minimum and maximum. Categorical variables will be summarized by counts and percentages.

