8.1.1 Analysis Population

Both, the ITT set and the safety set include all subjects who received at least one dose of study medication.

No per protocol analysis will be done.

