## **10.0 Efficacy Analysis**

### **10.1 General Considerations**

The subsequently described analyses will be provided in the ITT set. All statistical analyses will be descriptive. Results will be stratified between subjects who entered into the study with active versus inactive uveitis. For subjects who had inactive and subjects who had active uveitis when they entered the study, the efficacy analyses will start at Baseline of Study M11-327. Results will also be provided overall except for efficacy variables defined differently for subjects entering Study M11-327 with active and inactive uveitis.

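### SAP 5.1 calls its efficacy set ITT but drops dosed subjects for eye surgery or diabetic eye disease arising during the study, contrary to the protocol's all-dosed definition

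*SAP*

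**What the plan says.** The protocol defines the efficacy population twice, in the same way. The synopsis refers to the "Intent to Treat (ITT) set which includes all subjects that received at least one dose of study drug in Study M11-327". Section 8.1.1 makes the ITT and safety sets identical and adds "No per protocol analysis will be done".

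SAP 5.1 also opens with an all-dosed ITT definition, but continues "In addition, the following subjects will be excluded from the ITT set" and lists five groups:

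- subjects who develop Exclusion Criterion 5 (diabetic eye disease) during the study;
- "Subjects undergoing a cataract surgery during the study";
- "Subjects that had previous vitrectomy or are vitrectomized during the study";
- specified subjects of one French investigator, who "will be excluded because of incomplete efficacy source data in studies M10-877 and M10-880";
- subjects of one US investigator, for compliance problems in the parent studies.

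The demographic and baseline tables (SAP 7.0) and all efficacy analyses (SAP 10.1) use this set. The disposition table in SAP 8.0 still describes the ITT row as dosed subjects, with no mention of exclusions. Safety analyses (SAP 11.0) use the unrestricted safety set.

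**The concern.** The first two groups, and half of the third, are defined by something that happens after dosing starts. Three consequences follow.

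1. **Membership depends on the future.** A subject operated on late in follow-up vanishes from the baseline tables and from every earlier visit. SAP 6.3 and 8.0 allow for an interim analysis, so a subject counted there could be missing from the final table for the same visit.
2. **Valid data are discarded.** The whole subject leaves every efficacy variable, including steroid dose, immunosuppression load, work productivity and resource use. Eye surgery does not invalidate those measures, nor any measure taken before it.
3. **Some subjects bypass non-responder imputation.** An excluded subject who also drops out or misses visits would have counted as a non-responder under SAP 6.3.1, and now does not count at all.

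The excluding events need not be unrelated to outcome. Protocol 6.1.1.1.1 lists cataracts and vision loss among uveitis-related events, and Protocol 3.4 names cataract as a corticosteroid side effect, while steroid dose is itself an efficacy variable. At stake is whether the reported proportions and their 95% confidence intervals describe the population that the protocol named.

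**Working it through.** The plan contains no power calculation or derived figure to reproduce; Protocol 8.2 ties sample size to the number of rollovers. The check is a comparison of texts, followed by an identity for the bias.

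**Texts side by side**

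| Place | ITT set |
|---|---|
| Protocol 1.2 and 8.1.1 | all dosed, same as safety set |
| SAP 5.1, first sentence on ITT | all dosed |
| SAP 5.1, list that follows | all dosed minus five groups |
| SAP 8.0, row label | all dosed |

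The SAP list conflicts with the protocol and with two other statements in the SAP.

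**Bias.** The all-dosed proportion is (1 − f)p + fq. The restricted set reports p. The shift (reported minus all-dosed) is therefore p − [(1 − f)p + fq] = f(p − q). It is positive if excluded subjects respond less than those kept, negative if they respond more, and zero if they respond equally.

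**Inputs.** N of about 400 is the protocol's estimate. The values of f, p and q, and equal strata of 200, are assumptions. The half-width is 1.96 × √[p(1 − p)/n], with n the number kept.

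With p = 0.60 and q from 0 to 0.90:

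| f | Shift, points | Half-width, pooled (n) | Half-width, one stratum of 200 (n) |
|---|---|---|---|
| 5% | +3.0 to −1.5 | 4.9 (380) | 7.0 (190) |
| 10% | +6.0 to −3.0 | 5.1 (360) | 7.2 (180) |
| 20% | +12.0 to −6.0 | 5.4 (320) | 7.6 (160) |

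The stratum column matters because SAP 10.1 says "Results will be stratified between subjects who entered into the study with active versus inactive uveitis"; pooled results are also planned for variables defined alike in both groups.

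How the shift compares with sampling error depends on p, so no general threshold can be given:

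- p = 0.90, f = 0.05, pooled n = 380: half-width 1.96 × √(0.09/380) = 3.0 points. The shift exceeds it when q < 0.90 − 0.030/0.05, about 30%. At p = 0.60 with the same f, it cannot.
- p = 0.30, f = 0.20, q = 0.90, stratum n = 160: shift 0.20 × (0.30 − 0.90) = −12 points, against 1.96 × √(0.21/160) = 7.1 points. At p = 0.60 with the same f and q, the downward shift is only −6.0 against 7.6.

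**Data loss, one example.** Surgery at Week 200 removes the visits at Weeks 0, 2, 4, 8, 12 and 18 (6) and those from Week 30 to Week 198 every 12 weeks, (198 − 30)/12 + 1 = 15. That is 21 scheduled visits before the event.

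**The case against.** The best defence is that cataract surgery or vitrectomy can itself change acuity or gradings, so later values may not reflect the drug. That is a fair reason to handle post-surgery eye measures separately. It is not stated in the SAP, and it does not justify removing pre-surgery data or variables that are not eye measurements. Protocol 5.3.1.1 also provides for pseudophakic subjects, so an operated lens is not in itself disqualifying.

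Other points stand and limit the finding:

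- SAP 8.0 already plans counts for both sets, so the total excluded should be visible if the row follows 5.1. The breakdown by reason and by active/inactive group is not described.
- The table list is a separate document (SAP 12.0) not available here. One can say only that the SAP text describes no all-dosed efficacy analysis.
- Entry criteria 2 and 5 screen out likely cataract surgery and severe diabetic retinopathy, so f may be small.
- Both investigator exclusions have stated reasons from the parent studies. Previous vitrectomy is history, not an event during follow-up. These depart from Protocol 8.1.1 but do not make membership depend on later events.

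A reader might infer that every excluded subject escapes non-responder imputation. That is not supported: imputation acts only on missing values, and Protocol 5.4.1 does not list either operation as a reason for withdrawal. A subject who has surgery and stays has observed data. A reader might also infer a late, data-driven change. The SAP's Amendment 2 change list does not include section 5.1, so nothing shows that the exclusions were introduced then.

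**Conclusion.** The contradiction is real and should be fixed. The efficacy set is not the one the protocol defines, it carries the same name, and part of it is defined by events after dosing.

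It may be tempting to conclude that efficacy is overstated. The documents do not support that: the sign of f(p − q) is open, and f, p and q are all unknown. Nor can the shift be called always smaller, or always larger, than sampling error, since the comparison reverses with the assumed response rate. The illustration of +6 to −3 points rests entirely on the assumptions p = 60%, f = 10% and q from 0 to 90%.

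The importance is moderate. Efficacy is a secondary objective analysed descriptively, with no hypothesis test, and the primary safety analysis in all dosed subjects is unaffected.

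**What to change.** - **Main analysis.** Use the protocol's all-dosed set as ITT for efficacy and for the SAP 7 tables. Keep all data up to the event, and keep later data as observed.
- **Post-surgery values.** Add one sensitivity analysis that leaves out post-event values of surgery-affected eye measures. State that these are not evaluable and are not turned into non-response by NRI. Many endpoints need both eyes, so without this statement one unevaluable eye would make the subject a non-responder.
- **Restricted set.** Give the present set another name and report it as a sensitivity analysis.
- **Counts.** Beyond those already planned in SAP 8.0, report numbers excluded by reason and by active/inactive group. Correct the row label there.
- **Previous vitrectomy and the two investigators.** Document these as a departure from Protocol 8.1.1, or show results with and without those subjects. Parent-study visits can supply the M11-327 baseline (Protocol 5.3.1.1), so incomplete parent-study source data can affect it.

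The cost is SAP wording and a few extra table runs. Some efficacy figures may move, in either direction.
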